10.2.5 Exceptions to AE & SAE Definitions

Generally speaking, any adverse event that results in hospitalization or prolonged hospitalization should be documented and reported as an SAE, as described above. Likewise, any condition responsible for surgery should be documented as an AE if the condition meets the criteria for an AE. However, for the purposes of this study, neither the condition, hospitalization, prolonged hospitalization, nor surgery are reported as AEs or SAEs under the following circumstances:

10.2.5.1 Hospitalization or prolonged hospitalization is for a diagnostic or elective surgical procedure for a preexisting condition. Surgery should not be reported as an outcome of an adverse event if the purpose of the surgery was elective or diagnostic and the outcome was uneventful.

10.2.5.2 Hospitalization or prolonged hospitalization is required to allow efficacy measurement for the study.

10.2.5.3 Hospitalization or prolonged hospitalization is required for study-directed therapy of the target disease of the study, unless it is a worsening or increase in frequency of hospital admissions as judged by the principal investigator.

10.2.5.4 Hospitalization or prolonged hospitalization is due to social reasons (i.e. awaiting transport home).

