10.2 Definitions & Descriptions

10.2.1 Adverse Event

An AE is any untoward medical occurrence in a patient receiving study treatment and which does not necessarily have a causal relationship with this treatment. An AE can therefore be any unfavorable and unintended sign (including an abnormal laboratory finding), symptom, or disease temporarily associated with the use of an experimental intervention, whether or not related to the intervention.

Recording of AEs should be done in a concise manner using standard, acceptable medical terms. In general, AEs are not procedures or measurements, but should reflect the reason for the procedure or the diagnosis based on the abnormal measurement. Preexisting conditions that worsen in severity or frequency during the study should also be recorded (a preexisting condition that does not worsen is not an AE). Further, a procedure or surgery is not an AE; rather, the event leading to the procedure or surgery is considered an AE.

If a specific medical diagnosis has been made, that diagnosis or syndrome should be recorded as the AE whenever possible. However, a complete description of the signs, symptoms and investigations which led to the diagnosis should be provided. For example, if clinically significant elevations of liver function tests are known to be secondary to hepatitis, “hepatitis” and not “elevated liver function tests” should be recorded. If the cause is not known, the abnormal test or finding should be recorded as an AE, using appropriate medical terminology (e/g/ thrombocytopenia, peripheral edema, QT prolongation).

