10.2.3 Serious Adverse Event

An SAE is any untoward medical occurrence i.e. an undesirable sign or symptom or medical condition that at any dose results in one of the following outcomes:

- 10.2.3.1 Death:** if death results from progression of the disease, the disease progression should be reported as an SAE itself.
- 10.2.3.2 A life-threatening adverse event:** the patient was at risk of death at the time of the event (this does not refer to an event that hypothetically might have caused death if it were more severe).
- 10.2.3.3 A congenital anomaly/birth defect.**
- 10.2.3.4 A persistent or significant incapacity** or substantial disruption of the ability to conduct normal life functions.
- 10.2.3.5 An adverse event that requires inpatient hospitalization or prolongation of existing hospitalization for ≥ 24 hours,** unless hospitalization is for:
 - 10.2.3.5.1** Routine treatment or monitoring of the studied indication, not associated with any deterioration in condition (specify what this includes).
 - 10.2.3.5.2** Elective or pre-planned treatment for a pre-existing condition that is unrelated to the indication under study and has not worsened since the start of study drug.
 - 10.2.3.5.3** Treatment on an emergency outpatient basis for an event not fulfilling any of the definitions of a SAE given above and not resulting in hospital admission.
 - 10.2.3.5.4** Social reasons and respite care in the absence of any deterioration in the patient's general condition.
- 10.2.3.6 Is medically significant or is an important medical event,**

Important medical events are those that may not meet any of the above criteria, but that are clearly of major clinical significance in the judgment of the investigator. They may jeopardize the subject, and/or may require intervention to prevent one of the other serious outcomes noted above. Examples might include: allergic bronchospasm requiring intensive treatment in an emergency room or at home, convulsions that may not result in hospitalization, or development of drug abuse or drug dependency.

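### The exception in 10.2.5.1 for diagnostic or elective surgical admissions has no limit for a preexisting condition that worsened on study, so it conflicts by omission with 10.2.1 and 10.2.3.5.2

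*Combined protocol and SAP*

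**What the plan says.** Three parts of section 10 of the combined protocol and SAP bear on the same kind of event.

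- **10.2.1 (Adverse Event).** "Preexisting conditions that worsen in severity or frequency during the study should also be recorded". The same paragraph adds that a preexisting condition which stays the same is not an AE. It also says that a procedure is not an AE, but the event that led to it is.
- **10.2.3.5.2 (Serious Adverse Event).** An adverse event requiring inpatient admission is an SAE, with listed exclusions. One exclusion is elective or pre-planned treatment, but only for a "pre-existing condition that is unrelated to the indication under study and has not worsened since the start of study drug".
- **10.2.5 (Exceptions to AE & SAE Definitions).** The lead-in first repeats the ordinary rule that "any condition responsible for surgery should be documented as an AE if the condition meets the criteria for an AE". It then turns, for this study, to the exceptions: "neither the condition, hospitalization, prolonged hospitalization, nor surgery are reported as AEs or SAEs under the following circumstances". Item 10.2.5.1 reads: "Hospitalization or prolonged hospitalization is for a diagnostic or elective surgical procedure for a preexisting condition". A second sentence says when surgery is not to be listed as the result of an AE: "if the purpose of the surgery was elective or diagnostic and the outcome was uneventful".

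Item 10.2.5.3, on admissions for study-directed therapy of the target disease, does carry a limit: "unless it is a worsening or increase in frequency of hospital admissions as judged by the principal investigator".

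**The concern.** The exception is worded without qualification, and its lead-in covers the condition as well as the admission. Read literally, a preexisting condition that worsened on study drug and led to elective surgery is not reported at all. Sections 10.2.1 and 10.2.3.5.2 would have it recorded and, if it meets the hospitalization criterion, reported as serious.

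This matters because the safety and toxicity profile is a phase II secondary objective (2.2.2.2). The safety analyses in 9.1.2 and 9.2.3 summarize recorded adverse events and laboratory results, and the DMC reviews the SAEs that sites report (10.3.1). Five sites apply these definitions (3.1). If sites resolve the conflict differently, classification varies by site for reasons unrelated to the drugs. The omission can only remove events.

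**Working it through.** No arithmetic applies, and the plan states no figure to reproduce. The check sets the rules side by side for each type of event.

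| Preexisting condition and setting | 10.2.1 | 10.2.3.5 with 10.2.3.5.2 | 10.2.5.1 with its lead-in | Result |
|---|---|---|---|---|
| Not worsened; diagnostic or elective surgical admission | Not an AE | Not an SAE, since there is no AE | Not reported | Agree |
| Worsened on study; diagnostic or elective surgical admission that meets 10.2.3.5 | AE | SAE | Neither the condition nor the admission is reported | **Conflict** |
| Worsened on study; emergency or medical admission that meets 10.2.3.5 | AE | SAE | Does not apply | Agree |
| Worsened on study; managed as an outpatient | AE | SAE only if another criterion in 10.2.3 is met | Does not apply | Agree |

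The second row rests on these steps.

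1. The condition worsened, so 10.2.1 makes it an AE.
2. The AE required admission, so 10.2.3.5 makes it an SAE unless an exclusion applies. The exclusion in 10.2.3.5.2 needs both limbs of "unrelated to the indication under study and has not worsened since the start of study drug". The second limb fails, so the exclusion is unavailable. If the surgery was diagnostic rather than treatment, 10.2.3.5.2 does not apply in the first place, with the same result.
3. Item 10.2.5.1 applies on its face: there was an admission, for a diagnostic or elective surgical procedure, for a preexisting condition. It has no worsening test.

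Next, does any other text restore the missing limit?

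- The ordinary rule in the 10.2.5 lead-in does not, because the exceptions are introduced as departures from it.
- The requirement of an uneventful outcome does not. It governs whether surgery is reported as an outcome of an adverse event, not whether the condition had worsened.
- Section 10.3 requires all SAEs to be reported regardless of attribution, but only once an event counts as an SAE, which is the point in dispute.
- Item 10.2.5.3 shows that the drafters wrote a worsening limit where they wanted one. Its absence from 10.2.5.1 may therefore be read as intended.
- No section states an order of precedence.

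The history of changes lists revisions to 10.2.1 and 10.2.3 under Amendment 6 and none to 10.2.5. That would fit an exception list never aligned with the revised definitions, but it is an inference and the conflict in the current text does not depend on it.

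**The case against.** The strongest reply is that 10.2.5.1 is silent on worsening and does not say that worsened conditions are exempt. A sensible site could record the worsening as the event that led to the procedure, as 10.2.1 directs, and exempt only the admission. That stands to this extent: the conflict is by omission, and some sites will read it that way. It does not settle the matter, because the lead-in to 10.2.5 names the condition among the things not reported.

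It is also fair that much on-study worsening would still be visible. The schedule of events includes toxicity assessments, vital signs, EKGs and laboratory tests, Table 7 requires action on named toxicities, and reasons for discontinuation are documented. These limit the loss but do not replace an AE or SAE report.

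A reader might infer more than the documents support:

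- **A general loss of cardiovascular or bleeding data.** The exception reaches only diagnostic or elective surgical admissions for a preexisting condition. A new infarction or stroke is outside it.
- **A size taken from the 3% arterial thrombotic rate in 1.4.2.** Nothing there describes those events as elective or diagnostic surgical admissions for a preexisting condition. That rate says nothing about how often the exception would apply.
- **An exemption for all diagnostic admissions, such as a non-surgical cardiac work-up.** The adjective most naturally describes surgery, and the next sentence of 10.2.5.1 speaks of the purpose of the surgery.
- **A separate gap for the tumor, because 10.2.5.1 also lacks the limit to conditions unrelated to the indication.** An unworsened tumor is not an AE under 10.2.1, so 10.2.3.5 is not reached and the missing limit changes nothing through that route. Only the worsening limb has substance.

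**Conclusion.** The point holds in a narrow form. For a preexisting condition that worsened on study and led to a diagnostic or elective surgical admission, 10.2.5.1 as written exempts what 10.2.1 and, where the admission criterion is met, 10.2.3.5.2 require to be reported. The sections must be reconciled.

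The direction of any error is known: toward under-reporting, possibly differing by site. Its size is not, because the documents give no count or rate of such admissions, and none should be supplied by assumption. As a unit only, one omitted patient event in a full phase II cohort of 27 lowers an observed proportion by 1/27 = 3.7 percentage points. That is not an estimate of how often this happens.

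The conclusion assumes that sites apply the lead-in and 10.2.5.1 as worded. It bears on the completeness of AE and SAE data for a secondary objective and for DMC review. It is worth correcting, but it does not undermine the trial's primary analysis.

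**What to change.** Amend the item numbered 10.2.5.1 under Exceptions to AE & SAE Definitions so that it covers only a preexisting condition that has not become worse since study drug was started, borrowing the second limb of "unrelated to the indication under study and has not worsened since the start of study drug". Add one sentence: a preexisting condition that has worsened is recorded as an AE under 10.2.1, and as an SAE if it meets 10.2.3. The amendment should cite the section by title, because the number 10.2.5.1 is used again in the UPIRSO section (10.2.6).

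The cost is a short text change and a few more AE and SAE reports. No dose, schedule or clinical rule changes. A look-back at admissions already treated as exempt is optional: exempt admissions generate no SAE form, and the documents describe no log of them, so it could mean chart review at five sites.

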10.2.6 Unanticipated Problem Involving Risk to Subject or Others (UPIRSO)

In order for an adverse event to be reported to the Northwestern University IRB, it must qualify as a UPIRSO. In order to qualify as a UPIRSO, the event must meet *all three* of the following criteria:

10.2.5.1 The event must be unanticipated in terms of nature, severity, or frequency (i.e. not described in study-related documents such as the IRB-approved protocol or consent form, the investigators brochure, etc.).

10.2.5.2 The event must place the research subject or others at a different or greater risk of harm (including physical, psychological, economic, or social harm).

10.2.5.3 The event must be *at least possibly* related to participation in the study.

10.3 Reporting of SAEs

All SAEs, regardless of attribution, occurring during the study or within 30 days of the last administration of temozolomide and/or pazopanib must be reported to the principal investigator upon discovery or occurrence. Additional expedited or routine reporting may be required, depending on the nature of the SAE (as outlined below). Please also refer to Table 7 – Summary of Hematologic & Non-Hematologic Dose Modifications for Pazopanib – for additional information regarding toxicities that should be reported as SAEs.

10.3.1 Reporting to the QAM/DMC

All SAEs must be reported to the assigned QAM within 24 hours of becoming aware of the event. Completion of the NU CRO SAE form is required (available as stand-alone document).

The completed form should assess whether or not the event qualifies as a UPIRSO. The report should also include:

- 10.3.1.1 Protocol description and number
- 10.3.1.2 The patient's identification number
- 10.3.1.3 A description of the event, severity, treatment, and outcome (if known)
- 10.3.1.4 Supportive laboratory results and diagnostics
- 10.3.1.5 The hospital discharge summary (if available/applicable)

All SAEs will be reported to, and reviewed by, the DMC at their next meeting.

10.3.2 Reporting to the Northwestern University IRB

The following information pertains to the responsibilities of the lead site (Northwestern University). Additional participating sites should follow their local IRB guidelines for reporting to their local IRBs.

- 10.3.2.1 Any death of an NU subject that is *unanticipated* in nature and at least *possibly related* to study participation will be promptly reported to the Northwestern University IRB within 24 hours of notification.
- 10.3.2.2 Any death of an NU subject that is actively on study treatment (regardless of whether or not the event is possibly related to study treatment)
- 10.3.2.3 The following SAEs will be reported to the NU IRB within 5 working days of notification:
 - 10.3.2.2.1 Death of a *non-NU subject* that is *unanticipated* in nature and at least *possibly related* to study participation
 - 10.3.2.2.2 Other UPIRSOs
- 10.3.2.4 The following SAEs will be reported to the NU IRB at the time of annual continuing review:
 - 10.2.3.4.1 All deaths of NU subjects that were not previously reported.

10.2.3.4.2 All deaths of non-NU subjects that are deemed to be unanticipated in nature *and unrelated* to participation.

10.2.3.4.3 All other SAEs not previously reported to the IRB as UPIRSOs

10.3.3 Reporting to Novartis

The principal investigator has the obligation to report all serious adverse events to Novartis Pharmaceuticals Drug Safety and Epidemiology Department (DS&E).

All events reported to the FDA by the investigator are to be filed utilizing the Form FDA 3500A (MedWatch Form).

To ensure patient safety, every SAE, regardless of suspected causality, occurring:

10.3.3.1 After the patient has provided informed consent and until atleast 30 days after the patient has stopped study treatment/participation.

10.3.3.2 After protocol-specified procedures begin (e.g., placebo run-in, washout period, double-blind treatment, etc.) and 30 days after the patient has stopped study treatment.

10.3.3.3 After the start of any period in which the study protocol interferes with the standard medical treatment given to a patient (e.g., treatment withdrawal during washout period, change in treatment to a fixed dose of concomitant medication) and until 30 days after the patient has stopped study treatment.

All events must be reported to Novartis within 24 hours of learning of its occurrence. Information about all SAEs is collected and recorded on a Serious Adverse Event Report Form (NU SAE form); all applicable sections of the form must be completed in order to provide a clinically thorough report. The investigator must assess and record the relationship of each SAE to each specific study treatment (if there is more than one study treatment), complete the SAE Report Form (NU SAE form) in English, and **send the completed, signed form by fax to ([contact]) within 24 hours to the oncology Novartis DS&E department with the provided FAX cover sheets** (available as stand-alone documents).

This includes serious, related, labeled (expected) and serious, related, unlabeled (unexpected) adverse experiences. All deaths during treatment or within 30 days following completion of active protocol therapy must be reported within 24 hours.

Any SAEs experienced after this 30 days period should only be reported to Novartis if the investigator suspects a causal relationship to the study drug. Recurrent episodes, complications, or progression of the initial SAE must be reported as follow-up to the original episode within 24 hours of the investigator receiving the follow-up information. An SAE occurring at a different time interval or otherwise considered completely unrelated to a previously reported one should be reported separately as a new event. The end date of the first event must be provided.

The original copy of the SAE Report and the fax confirmation sheet must be kept within the Trial Master File at the study site.

Follow-up information is sent to the same fax number as the original SAE Report Form was sent, using a new fax cover sheet, stating that this is a follow-up to the previously reported SAE, and giving the date of the original report. Each re-occurrence, complication, or progression of the original event should be reported as a follow-up to that event regardless of when it occurs. The follow-up information should describe whether the event has resolved or continues, if and how it was treated, whether the blind was broken or not (if applicable), and whether the patient continued or withdrew from study participation.

If the SAE is not previously documented in the Pazopanib Investigator Brochure or Package Insert (new occurrence) and is thought to be related to the Novartis study drug, a DS&E associate may urgently require further information from the investigator for Health Authority reporting. Novartis may need to issue an Investigator Notification (IN), to inform all investigators involved in any study with the same drug that this SAE has been reported. Suspected Unexpected Serious Adverse Reactions (SUSARs) will be collected and reported to the competent authorities and relevant ethics committees in accordance with Directive 2001/20/EC or as per national regulatory requirements in participating countries.

To ensure patient safety, each pregnancy occurring while the patient is on study treatment must be reported to Novartis within 24 hours of learning of its occurrence.

The pregnancy should be followed up to determine outcome, including spontaneous or voluntary termination, details of birth, and the presence or absence of any birth defects, congenital abnormalities or maternal and newborn complications.

Pregnancy should be recorded on a Clinical Study Pregnancy Form and reported by the investigator to the oncology Novartis Drug Safety and Epidemiology (DS&E) department. Pregnancy follow-up should be recorded on the same form and should include an assessment of the possible relationship to the Novartis study treatment of any pregnancy outcome. Any SAE experienced during pregnancy must be reported on the SAE Report Form (NU SAE form).

10.3.4 Reporting to NCCN

10.3.4.1 All SAEs must also be reported to NCCN via fax at [contact] or e-mailed to [contact]

10.3.4.2 The NU CRO SAE form will be used to report SAEs to NCCN. This form will include a full written summary, detailing relevant aspects of the adverse events in question. Where applicable, information from relevant hospital case records and autopsy reports should be included.

10.3.4.3 In addition, the Investigators will adhere to the safety reporting requirements and timelines described in the Clinical Trial Agreement with National Comprehensive Cancer Network (NCCN).

11.0 STUDY MANAGEMENT

11.1 Institutional Review Board (IRB) Approval and Consent

It is expected that the IRB will have the proper representation and function in accordance with federally mandated regulations. The IRB should approve the consent form and protocol.

In obtaining and documenting informed consent, the investigator should comply with the applicable regulatory requirement(s), and should adhere to Good Clinical Practice (GCP) and to ethical principles that have their origin in the Declaration of Helsinki.

Before recruitment and enrollment onto this study, the patient will be given a full explanation of the study and will be given the opportunity to review the consent form. Each consent form must include all the relevant elements currently required by the FDA Regulations and local or state regulations. Once this essential information has been provided to the patient and the investigator is assured that the patient understands the implications of participating in the study, the patient will be asked to give consent to participate in the study by signing an IRB approved consent form.

Prior to a patient's participation in the trial, the written informed consent form should be signed and personally dated by the patient and by the person who conducted the informed consent discussion.

11.2 Amendments

The Principal Investigator will formally initiate all amendments to the protocol and/or informed consent. All amendments will be subject to the review and approval of the appropriate local, institutional, and governmental regulatory bodies, as well as by Janssen Scientific Affairs. Amendments will be distributed by the lead institution (Northwestern) to all affiliate sites upon approval by the Northwestern University IRB.

